COVID-19 infection causes progressive severe lung infection that can lead to death in a significant number of infected patients. Prior work using allogeneic mesenchymal stem cells (MSCs) in severely infected individuals has shown promise in reversing the severe consequences of infection in critically ill patients. Thus, the potential exists for allogeneic MSCs to slow or halt disease progression and reduce time on ventilators in critically ill patients infected with COVID-19, and thus improve disease outcomes.

A total of 45 subjects receiving care in the critical care or ICU setting with mechanical ventilation for COVID-19 will be enrolled in this study. Subjects will be randomized 2:1 to the experimental arm (30 subjects) and control arm (15 subjects).

Subjects in the experimental arm will be administered BM-Allo.MSC ($0.7\text{-}1.3 \times 10^6$ cells/kg IV) on day 1 followed by day 5 (± 1 day), if subject still requires ventilation on day 5. Subjects will be followed through day 60. Subjects in the control arm will be administered placebo on a schedule identical to that of the experimental arm and followed through day 60.

BM-Allo.MSC and placebo may be provided to the clinical treatment site as a cryopreserved preparation. The cryopreserved product will contain BM-Allo.MSC in 5% albumin (human), USP, and CryoStor 10 (CS10) (in 1:1 ratio) in a volume of 100 mL. The placebo will consist of 5% albumin (human), USP, and CS10 (1:1 ratio) in a volume of 100 mL.

All subjects will be assessed using a 7-point ordinal scale that evaluates clinical status at the first assessment of each study day. The scale is as follows: 1) death; 2) hospitalized, on invasive mechanical ventilation or extracorporeal membrane oxygenation (ECMO); 3) hospitalized, on non-invasive ventilation or high-flow oxygen devices; 4) hospitalized, requiring supplemental oxygen; 5) hospitalized, not requiring supplemental oxygen; 6) not hospitalized, limitation on activities; 7) not hospitalized, no limitations on activities.

In addition, all subjects will be assessed using the standard National Early Warning Score (NEWS) score ([Royal College of Physicians 2012](#)). The NEWS score has demonstrated an ability to identify patients at risk of poor outcomes and will be used as a measure of efficacy. This score is based on 7 clinical parameters (respiration rate, oxygen saturation, any supplemental oxygen, temperature, systolic blood pressure, heart rate, level of consciousness).

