Safety will be assessed for all subjects and will include monitoring of vital signs and incidence and severity of adverse events. Blood samples will be collected for hematology and chemistry analyses.

Safety will be monitored throughout the study. After the first 5 subjects are randomized (giving at least 3 subjects in the experimental arm) enrollment will be paused and the NantKwest Safety Review Committee (SRC) will perform an evaluation of safety once the 5 subjects have completed the 14 day toxicity assessment period. Enrollment will continue if the safety evaluation from the initial 5 subjects suggests that the therapy is safe.

Primary Endpoints:

- Incidence of AEs within 30 days of randomization.
- Mortality within 30 days of randomization.
- Cause of death within 30 days of randomization
- Number of ventilator-free days within 60 days of randomization.

Secondary Endpoints:

- Time from randomization to an improvement of one category using the ordinal scale.
- Change in the 7-point ordinal scale from baseline.
- Change in NEWS from baseline.
- Time from randomization to discharge or to a NEWS of ≤ 2 maintained for 24 hours, whichever occurs first.
- Change from baseline in Sequential Organ Failure Assessment (SOFA) score on days 8, 15, 22, and 29.
- Number of days requiring oxygen.
- Duration of hospitalization from randomization.
- Incidence of SAEs within 30 days of randomization
- Change from baseline in hemoglobin, platelets, and white blood cell (WBC) count.
- Changes in vital signs from baseline.

Enrollment (planned):

A total of 45 subjects receiving care in the critical care or ICU setting with mechanical ventilation for COVID-19 will be randomized 2:1 to the experimental arm (30 subjects) and control arm (15 subjects) in this study.

Eligibility Criteria:***Inclusion Criteria:***

1. Age ≥ 18 years old.
2. Able to understand and provide a signed informed consent that fulfills the relevant Institutional Review Board (IRB) or Independent Ethics Committee (IEC) guidelines. For subjects that are intubated and/or sedated, or otherwise unable to provide consent, prospective consent from a legally-authorized representative is required. The subject or his/her legally authorized representative must be able to provide consent.

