Exclusion Criteria:

1. Known hypersensitivity to any component of the study medication(s), including dimethyl sulfoxide (DMSO).
2. Signs of multisystem organ failure. Liver function tests (LFTs) $> 5x$ normal.
3. Intubated > 72 continuous hours.
4. Assessed by the Investigator to be unable or unwilling to comply with the requirements of the protocol.
5. Pregnant and nursing women. A negative serum pregnancy test during screening (within 72 hours prior to the first dose) must be documented before MSCs are administered to a female subject of child-bearing potential.

Products, Dosage, and Mode of Administration:		
Investigational Products	Dosage	Mode of Administration
BM-Allo.MSC	$0.7\text{-}1.3 \times 10^6$ cells/kg	IV
Duration of Treatment:		
Subjects in the experimental arm will be administered BM-Allo.MSC ($0.7\text{-}1.3 \times 10^6$ cells/kg IV) on day 1 followed by day 5 (± 1 day), if subject still requires ventilation on day 5. Subjects will be followed through day 60. Subjects in the control arm will be treated with placebo on a schedule identical to that of the experimental arm and followed through day 60.		
Duration of Follow-up:		
Subjects who receive study treatment for any reason will be followed via regular visits with a health care professional until either death (by any cause) or for a minimum of 30 days after administration of BM-Allo.MSC.		
Reference Therapy, Dosage, and Mode of Administration:		
Subjects randomized to the control arm will receive an IV infusion of placebo, provided to the clinical treatment site as a cryopreserved preparation. The cryopreserved placebo consists of 5% albumin (human), USP, and CryoStor 10 (1:1 ratio) in a volume of 100 mL.		

Evaluation of Endpoints:

Safety: Safety endpoints include assessments of treatment-emergent AEs, SAEs, and changes in hemoglobin, platelets, and white blood cell (WBC) count safety laboratory tests and vital signs. Toxicities will be graded using CTCAE Version 5.0

Efficacy: Mortality and cause of death within 30 days of randomization, number of ventilator-free days within 60 days of randomization, number of subjects reporting each severity rating on the 7-point ordinal scale, and number of subjects with improved NEWS scores and 7-point ordinal scale.

Statistical Methods:

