All subjects receiving at least one dose of study drug (ie, the Safety population) will be included in the safety and efficacy analyses. Statistical analysis will be descriptive and presented by treatment arm. No statistical testing will be performed.

Safety Analyses:

Overall safety will be assessed by descriptive analyses using tabulated frequencies of AEs by grade using CTCAE version 5 in terms of treatment-emergent AEs, SAEs, and AEs by grade and clinically significant changes in safety laboratory tests and vital signs.

Efficacy Analyses:

The mortality rate within 30 days of randomization and 95% confidence interval will be summarized. Cause of death will be summarized. The mean number of ventilator-free days and number of days requiring oxygen within 60 days of randomization and the mean duration of hospitalization will be summarized.

Time from randomization to an improvement of one category on the 7-point ordinal scale will be summarized. The mean change from baseline on the 7-point ordinal scale at each post-baseline evaluation time point will be summarized.

The mean change from baseline for each parameter of NEWS and the overall score at each post-baseline evaluation time point will be summarized. Time from randomization to discharge or to a NEWS of ≤ 2 maintained for 24 hours, whichever occurs first will be summarized. The mean change from baseline in SOFA score at each post-baseline evaluation time point will be summarized.

Figure 1: Study Treatment Schema

[figure not shown]

Table 5: Schedule of Events

	Baseline/Screening ^a	Study Day						
		1	5	8	15	22	29	60/EOS
Study Day	-1 or 1	± 1						± 4
General Assessments								
Informed consent	X							
Inclusion/exclusion	X							
Demographics	X							
Medical history	X							
Confirm contraceptive measures	X							
APACHE assessment	X							
High-sensitivity CRP	X							
Physical exam: height, weight ^b	X	X	X					
Vital signs ^c	X	Daily, throughout study period						
SOFA assessment	X	X		X	X	X	X	X
Ordinal scale (7-point)	X	X		X	X	X	X	X
NEWS ^c	X	Daily, throughout study period						X
Concomitant medications ^c	X	Daily, throughout study period						X
Adverse event collection ^c	X	Daily, throughout study period						X

	Baseline/Screening ^a	Study Day						
Study Day	-1 or 1	1	5	8	15	22	29	60/EOS
Windows (days)		± 1						± 4
Study drug administration								
BM-Allo.MSC or Placebo		X	X ^d					
Laboratory Assessments								
Collect NP swabs	X	X						
Chemistry panel ^e	X	X		X	X	X	X	X

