Hematology ^f	X	X		X	X	X	X	X
Collect whole blood for immunogenicity and cytokine analyses	X	X		X	X	X	X	X
Pregnancy test ^g	X	X						

^a Baseline/screening assessments may be done ≤ 1 calendar day prior to the first dose of BM-Allo.MSC or placebo. Day 1 assessments do not need to be repeated if baseline/screening is done on study day 1. Assessments performed on day 1 must be performed before dosing.

^b Height required at baseline/screening visit only. Weight on day 1 should be used to calculate drug dose.

^c Vital signs, concomitant medications, NEWS assessment, and adverse event collection will occur daily throughout the study period (ie, each day beginning day 1 and continuing through day 29). Vital signs of temperature, heart rate, blood pressure, oxygen saturation, and respiratory rate will be assessed at every visit.

^d Dose to be administered on day 1 followed by day 5 (± 1 day), if subject still requires ventilation on day 5.

^e See [Table 4](#) for additional details on laboratory assessments. Blood draws for lab assessments should occur prior to BM-Allo.MSC or placebo administration.

^f Hematology to include CBC with differential (5 part) as outlined in Table 4. Blood draws for lab assessments should occur prior to BM-Allo.MSC or placebo administration.

[figure not shown]
^g Serum pregnancy tests for females of child-bearing potential.

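### Mean change in SOFA and NEWS at each visit covers only subjects alive and measured, so the arm with fewer deaths can look worse on these secondary endpoints

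*Combined protocol and SAP*

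**What the plan says.** The latest synopsis in the combined document (the placebo-controlled version with cryopreserved product) lists change in SOFA and change in NEWS as secondary endpoints. The SOFA endpoint reads "Change from baseline in Sequential Organ Failure Assessment (SOFA) score on days 8, 15, 22, and 29".

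Under Statistical Methods, Efficacy Analyses, the plan for SOFA is "The mean change from baseline in SOFA score at each post-baseline evaluation time point will be summarized" and for NEWS "The mean change from baseline for each parameter of NEWS and the overall score at each post-baseline evaluation time point will be summarized".

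Table 5 schedules SOFA on days 8, 15, 22, 29 and 60/EOS. Its footnote c puts NEWS on a daily schedule, "each day beginning day 1 and continuing through day 29", with a further assessment at day 60/EOS.

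The Study Design section builds NEWS from seven clinical parameters, none of which is a death state. It does not describe the components of SOFA. The 7-point ordinal scale, by contrast, makes death category 1.

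The Duration of Follow-up entry has subjects followed "until either death (by any cause) or for a minimum of 30 days after administration of BM-Allo.MSC". Statistical Methods says that all dosed subjects enter the safety and efficacy analyses, that results are descriptive by arm, and that nothing is tested.

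**The concern.** A visit mean of SOFA or NEWS cannot include a subject who has died unless a rule says how. The supplied text has no such rule: no assigned score, no ranking, and no statement that the mean applies only to the living. This sits badly with the statement that every dosed subject is in the efficacy analyses.

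Deaths are unlikely to be rare. Subjects are ventilated with moderate or severe ARDS, 30-day mortality is a primary endpoint, and the Study Design section says: "COVID-19 infection causes progressive severe lung infection that can lead to death in a significant number of infected patients".

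The subjects averaged at later visits are therefore selected by outcome. If the arms differ in mortality, they differ in that selection. An arm that keeps very sick subjects alive carries their scores, while the other arm loses such subjects from its denominator. The effect also runs the other way: a product that caused deaths among the sickest could show better SOFA and NEWS among those left, which matters in a study with a primary safety objective.

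**Working it through.** **Inputs from the documents.** 45 subjects randomized 2:1, that is 45 × 2/3 = 30 experimental and 45 × 1/3 = 15 control. No mortality rate, SOFA change, SD or power is stated, so the plan has no figure of its own to reproduce on this point.

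**Assumed inputs.** mC and mT are control and experimental mortality by the visit. a = −4 is the mean SOFA change in subjects who would survive on either arm, with no treatment effect on it. s is the mean change in subjects alive only because of treatment, taken as −2, 0 or +2.

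**Size of the shift.**

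- Control survivor mean = a.
- Experimental survivor mean = [(1 − mC)a + (mC − mT)s] / (1 − mT).
- Difference, experimental minus control = (mC − mT)(s − a) / (1 − mT).

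A positive difference makes the experimental arm look worse. If s = a, it is zero. With s = 0:

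| Control mortality | 10-point reduction | 20-point reduction |
|---|---|---|
| 30% | 0.10 × 4 / 0.80 = +0.50 | 0.20 × 4 / 0.90 = +0.89 |
| 40% | 0.10 × 4 / 0.70 = +0.57 | 0.20 × 4 / 0.80 = +1.00 |
| 50% | 0.10 × 4 / 0.60 = +0.67 | 0.20 × 4 / 0.70 = +1.14 |
| 60% | 0.10 × 4 / 0.50 = +0.80 | 0.20 × 4 / 0.60 = +1.33 |

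Over all values of s the range runs from 0.10 × 2 / 0.80 = +0.25 to 0.20 × 6 / 0.60 = +2.00. The expected number scored is 15 to 27 of 30 experimental subjects and 6 to 10.5 of 15 controls.

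A simulation at 30 versus 15 (s = 0, within-group SD 3 assumed, 10,000 trials per setting) had the experimental survivor mean worse in 66–69% of trials for a 10-point reduction and 78–81% for a 20-point reduction, against 50% with no mortality effect.

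**Which remedy works.** Take a second assumed case at day 29. In control, half die and survivors change by −6. In the experimental arm, half change by −6, a further 20% survive with −1, and 30% die.

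- Survivor means: control −6.0; experimental (0.5 × −6 + 0.2 × −1) / 0.7 = −4.6. The better arm looks 1.4 points worse.
- Medians with deaths given a worst score (assumed maximum 24, baseline 10, so +14): the experimental arm has 15 at −6, 6 at −1 and 9 at +14, so its median is (−6 − 1)/2 = −3.5. Half of 15 is 7.5 control deaths. With 7, the control median is −6 and the better arm still looks worse; with 8 it is +14. One death moves it by 20 points.
- Probability that an experimental subject ranks better than a control subject, death worst, ties counted as half:
  - 7 control deaths: 0.5 × (4 + 7)/15 + 0.2 × 7/15 + 0.3 × 3.5/15 = 7.95/15 = 0.53.
  - 8 control deaths: 0.5 × (3.5 + 8)/15 + 0.2 × 8/15 + 0.3 × 4/15 = 8.55/15 = 0.57.

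The ranking favours the better arm in both.

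**Discharge.** Suppose 30% die in each arm; arm A has 60% discharged and 10% in hospital, arm B 20% and 50%. If deaths are scored and discharged subjects left out, the dead make up 30/40 = 75% of those scored in A and 30/80 = 37.5% in B. The arm that discharges more looks worse, so discharged subjects must be in any death-inclusive summary.

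**The case against.** The strongest reply is that little depends on these two endpoints. They are secondary and descriptive in a 45-subject phase 1b study with no testing. Mortality is a primary endpoint reported with a 95% confidence interval, and change on the ordinal scale, which has a category for death, is summarized in the same section. All of this stands and limits the weight of the point. It does not remove it: a separate 30-day rate neither shows how many subjects stand behind each visit mean nor corrects that mean's direction.

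A reader might infer that the plan will reverse the order of the arms. The documents do not support that. Reversal needs a mortality difference and also worse scores in the subjects kept alive than in other survivors, and the documents give no data on either. Exclusion of subjects with signs of multisystem organ failure also makes it uncertain how large SOFA changes will be.

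A reader might also infer that discharged subjects will routinely lack SOFA. That is not shown: follow-up is by regular visits with a health care professional, ability to attend visits is an inclusion criterion, and laboratory draws share the SOFA days. Daily NEWS at home looks harder, and no rule covers it.

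Finally, the supplied text consists of synopses and schedules, so a rule for deaths could exist elsewhere. If it does, the synopsis should agree with it.

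**Conclusion.** The point holds in limited form. As written, the visit means for SOFA and NEWS are conditional on being alive and measured, and the plan does not say so. They can count against the arm with fewer deaths, by about 0.25 to 2 SOFA points under assumed mortality reductions of 10 to 20 points, with subjects kept alive scoring 2 to 6 points worse than other survivors. The shift vanishes if those subjects score like the rest. Every mortality rate, SOFA change, SD, baseline and maximum score used here is an assumption. The same size cannot be given for NEWS, which was not calculated. It would be too strong to say that the trial's efficacy reading is invalid or that deaths are hidden. The change is worth making because it is cheap and arm-by-arm means will be read as signals of efficacy even without a test.

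**What to change.** 1. At each scheduled visit and by arm, show the number dead, discharged alive, measured, and missing for other reasons.
2. Keep the planned mean change, labelled as conditional on being alive and measured.
3. Add one descriptive summary for SOFA and for total NEWS that ranks the dosed subjects at each visit: death worst, discharged alive without a score best, measured subjects in between. Report the distribution over these categories, or the probability that an experimental subject ranks better than a control subject. State in advance how a subject in hospital with no score is handled.

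Do not rely on a worst-score change summarized by a median alone, and do not leave discharged subjects out while deaths are scored.

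The cost is analysis wording and one extra table, with no change to data collection, sample size or treatment. The ranking treats all deaths alike and places a subject discharged without a score above one discharged with a score; a footnote should say so.

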Title of Study: Phase 1b Randomized, Double-Blind, Placebo-Controlled Study of the Safety of Therapeutic Treatment with Immunomodulatory Mesenchymal Stem Cells in Adults with COVID-19 Infection Requiring Mechanical Ventilation
Study Number: QUILT-COVID-19-MSC
Study Phase: Phase 1b

Study Objectives:Primary Objectives:

- To evaluate preliminary safety of BM-Allo.MSC vs placebo in terms of adverse events within 30 days of randomization.
- To evaluate preliminary efficacy of BM-Allo.MSC vs placebo in subjects who have tested positive for SARS-CoV-2 (COVID-19) and require ventilator support, as assessed by:
 - Mortality and cause of death within 30 days of randomization.
 - Number of ventilator-free days within 60 days of randomization.

Secondary Objectives:

- To further evaluate preliminary efficacy of BM-Allo.MSC vs placebo in subjects who have tested positive for SARS-CoV-2 (COVID-19), as assessed by:
 - Time from randomization to an improvement of one category in the 7-point ordinal scale.
 - Change in the 7-point ordinal scale from baseline.
 - Change in National Early Warning Score (NEWS) from baseline.
 - Time from randomization to discharge or to a NEWS of ≤ 2 maintained for 24 hours, whichever occurs first.
 - Change from baseline in Sequential Organ Failure Assessment (SOFA) score on days 8, 15, 22, and 29.
 - Number of days requiring oxygen within 60 days of randomization.
 - Duration of hospitalization from randomization.
- To further evaluate the safety of BM-Allo.MSC in subjects who have tested positive for SARS-CoV-2 (COVID-19), as assessed by:
 - Incidence of SAEs within 30 days of randomization.
 - Change from baseline in hemoglobin.
 - Change from baseline in platelets.
 - Change from baseline in white blood cell count.
 - Change from baseline in vital signs.

Study Design:

This is a phase 1b randomized, double-blind, placebo-controlled study in adult subjects with Coronavirus Disease 2019 (COVID-19). This clinical trial will evaluate the preliminary safety and efficacy of BM-Allo.MSC vs placebo in treating subjects with severe disease requiring ventilator support during COVID-19 infection. Only subjects with moderate or severe ARDS (per Berlin criteria; see [Appendix 1](#)) will be enrolled in this study.

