3. Has laboratory-confirmed positive novel coronavirus (SARS-CoV-2) test, as determined by polymerase chain reaction (PCR), or other commercial or public health assay in any specimen < 72 hours prior to enrollment, or meets the criteria to guide the evaluation and testing of patients under investigation (PUI) for COVID-19 (<https://emergency.cdc.gov/han/2020/HAN00428.asp>).

4. Requiring mechanical ventilatory support with moderate to severe Acute Respiratory Distress Syndrome (ARDS) as determined by the Berlin criteria:
 - a. Bilateral opacities present on a chest radiograph or computed tomographic (CT) scan. These opacities are not fully explained by pleural effusions, lobar collapse, lung collapse, or pulmonary nodules.
 - b. Origin of Edema: Respiratory failure not fully explained by cardiac failure or fluid overload.
 - c. Oxygenation: Moderate to severe impairment of oxygenation must be present, as defined by the ratio of arterial oxygen tension to fraction of inspired oxygen ($\text{PaO}_2/\text{FiO}_2$). The severity of the hypoxemia defines the severity of the ARDS:
 - Moderate: $\text{PaO}_2/\text{FiO}_2 > 100 \text{ mmHg}$ and $\leq 200 \text{ mmHg}$, on ventilator settings that include $\text{PEEP} \geq 5 \text{ cm H}_2\text{O}$
 - Severe: $\text{PaO}_2/\text{FiO}_2 \leq 100 \text{ mmHg}$ on ventilator settings that include $\text{PEEP} \geq 5 \text{ cm H}_2\text{O}$
- Subjects receiving extracorporeal membrane oxygenation (ECMO) will not be enrolled in this study.
5. High-sensitivity C-reactive Protein (hs-CRP) serum level $> 4.0 \text{ mg/dL}$
6. Acute Physiology and Chronic Health Evaluation (APACHE IV) score > 5
7. Agrees to the collection of nasopharyngeal (NP) swabs and venous blood per protocol.
8. Ability to attend required study visits and return for adequate follow-up, as required by this protocol.
9. Agreement to practice effective contraception for female subjects of child-bearing potential and non-sterile males. Female subjects of child-bearing potential must agree to use effective contraception while on study and for at least 1 month after the last dose of BM-Allo.MSC. Non-sterile male subjects must agree to use a condom while on study and for up to 1 month after the dose of BM-Allo.MSC. Effective contraception includes surgical sterilization (eg, vasectomy, tubal ligation), two forms of barrier methods (eg, condom, diaphragm) used with spermicide, intrauterine devices (IUDs), oral contraceptives, and abstinence.

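### Baseline SOFA, NEWS and blood counts are subtracted in change scores but not named as covariates, and no between-arm estimate is given for a comparison with placebo

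*Combined protocol and SAP*

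**What the plan says.** The documents hold three synopses; this point concerns the last one (double-blind, placebo-controlled, cryopreserved product).

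- **Objective.** The efficacy part of the primary objective is comparative: "To evaluate preliminary efficacy of BM-Allo.MSC vs placebo in subjects who have tested positive for SARS-CoV-2 (COVID-19) and require ventilator support". The secondary efficacy objective, which covers NEWS and SOFA, is also worded against placebo.
- **Size.** 45 subjects are randomized 2:1, 30 to BM-Allo.MSC and 15 to placebo (Study Design).
- **Framework.** Under Statistical Methods: "Statistical analysis will be descriptive and presented by treatment arm. No statistical testing will be performed".
- **SOFA and NEWS.** Efficacy Analyses gives "The mean change from baseline in SOFA score at each post-baseline evaluation time point will be summarized" and "The mean change from baseline for each parameter of NEWS and the overall score at each post-baseline evaluation time point will be summarized".
- **Blood counts.** A secondary endpoint is "Change from baseline in hemoglobin, platelets, and white blood cell (WBC) count".
- **Mortality.** "The mortality rate within 30 days of randomization and 95% confidence interval will be summarized".
- **Baseline data.** Table 5 schedules SOFA, NEWS, hematology, APACHE and hs-CRP at baseline/screening, and its footnote a requires day 1 assessments to precede dosing. ARDS category follows from the entry PaO2/FiO2 (inclusion criterion 4c): "The severity of the hypoxemia defines the severity of the ARDS".

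The synopsis names no covariate, stratification factor or between-arm estimator.

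**The concern.** A reader with a comparative objective and two columns of mean change will subtract one from the other. That contrast has two weaknesses.

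First, subtracting the baseline removes its influence completely only if baseline and follow-up are perfectly correlated (with equal variances). Otherwise the arm that starts worse by chance tends to show more improvement through regression to the mean, and this can look like a treatment effect or hide one.

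Second, the raw-change contrast is less precise than a baseline-adjusted one at the moderate correlations that are plausible over days to weeks in ventilated patients (an assumption). With 15 controls, both matter more than they would in a large trial. The data needed to deal with both are already collected for these endpoints.

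**Working it through.** **Inputs from the documents.** N = 45, arms of 30 and 15. The split agrees with the ratio: 45 × 2/3 = 30 and 45 × 1/3 = 15. The synopsis gives no SD, correlation, event rate or power, so N itself cannot be reproduced.

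**Assumed inputs.** Baseline to follow-up correlation r of 0.3, 0.5 or 0.7; equal SD at both times; a follow-up value for all 45. Results are in units of that SD.

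**Step 1: chance baseline difference.** SE = √(1/30 + 1/15) = √0.1 = 0.316 SD. P(|difference| > 0.5 SD) = P(|Z| > 0.5/0.316) = P(|Z| > 1.58) = 11%. For 0.25 SD it is 43%.

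**Step 2: effect on the raw-change contrast.** A baseline difference d carries forward as r·d on average, so the change contrast moves by r·d − d = −(1 − r)d. For d = 0.5 the size is 0.5 × 0.7 = 0.35, 0.5 × 0.5 = 0.25 and 0.5 × 0.3 = 0.15 SD at r = 0.3, 0.5 and 0.7.

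**Step 3: precision.**
- Change scores: variance = 2(1 − r) × 0.1.
- ANCOVA with one covariate: variance = (1 − r²) × 0.1 × (1 + 1/41). The last factor, with 41 = 45 − 4, is the cost of estimating the slope.

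| r | SE, change | SE, ANCOVA | Variance ratio | Reduction | N at which change matches ANCOVA on 45 |
|---|---|---|---|---|---|
| 0.3 | 0.374 | 0.305 | 0.67 | 33% | 68 |
| 0.5 | 0.316 | 0.277 | 0.77 | 23% | 59 |
| 0.7 | 0.245 | 0.229 | 0.87 | 13% | 52 |

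At r = 0.9 the ratio is 0.97, so the gain nearly vanishes.

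**Step 4: fewer subjects at late visits.** If only 18 versus 9 had a late SOFA value (assumed), the SE of the baseline difference would be √(1/18 + 1/9) = 0.408 SD and P(> 0.5 SD) would be 22%.

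**Step 5: mortality.** The crude and one-covariate-adjusted risk differences (logistic standardization) were simulated with 6,000 runs per setting. At an assumed 40% mortality the 95% half-width moves from 30.4 points to 29.9, 28.1 or 26.2 points for a covariate with AUC 0.64, 0.74 or 0.81. Over assumed mortality of 20% to 60%, the variance falls by only about 1% to 4% at AUC 0.64.

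**The case against.** The strongest reply is that the plan is descriptive, performs no test and defines no between-arm contrast, so no stated error rate or conclusion is harmed. Chance imbalance is sampling variability, not bias. This stands as a limit on severity. It does not dispose of the point: the objective is a comparison with placebo, an adjusted difference with a CI is an estimate and not a test, and the plan already reports a CI for mortality.

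A reader might infer more than the documents support:

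- **That the baselines go unused.** They do not: SOFA, NEWS and blood-count baselines are subtracted. What is missing is their use as covariates.
- **That adjustment would tighten the mortality figures in the plan.** The synopsis specifies a rate with a CI, presented by arm. Adjustment does not narrow single-arm intervals, and step 5 shows that it helps the difference little unless the covariate is strongly prognostic.
- **That a serious imbalance in ARDS severity is likely.** If 15 to 30 of the 45 subjects have severe ARDS (assumed), the arms differ by at least 20 percentage points with probability 19% to 34%. The upper figures depend on ties at exactly 20 points; for strictly more than 20 the range is 9% to 21%. The documents give no basis for turning such a gap into a mortality effect.
- **That the randomization is unstratified.** Only synopsis text is available and the schema figure is not shown, so stratification or adjustment set out elsewhere cannot be ruled out.

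Two further limits stand. SOFA cannot be scored after death, and ANCOVA does not repair that: later visits compare survivors. Also, ARDS category has no row of its own in Table 5, although the entry PaO2/FiO2 must be known for eligibility.

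**Conclusion.** The point holds as a small, specific improvement. The synopsis pairs a comparative objective with raw mean changes by arm, and names neither a between-arm estimate nor a baseline covariate. For r between 0.3 and 0.7, ANCOVA cuts the variance of the difference by about 33% to 13% and removes a shift of 0.35 to 0.15 SD for each 0.5 SD of chance baseline imbalance, an imbalance that is exceeded in about one trial in nine.

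These figures rest on assumed correlations, equal variances, a linear relation to baseline and complete follow-up. The case for adjusting mortality is weaker and optional. Nothing here invalidates the descriptive design.

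**What to change.** Before unblinding, add to the analysis text:

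1. For SOFA, NEWS, hemoglobin, platelets and WBC, keep the by-arm summaries and report beside them the between-arm difference with a 95% CI from ANCOVA, with the baseline value of the same measure as covariate. Label it descriptive. For visits after deaths have occurred, label it conditional on survival.
2. Optionally, and as a supportive figure only, report one severity-adjusted 30-day mortality difference with a single covariate fixed in advance, for example APACHE IV or ARDS category from the entry PaO2/FiO2. State that the gain in precision is small unless that covariate is strongly prognostic.

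The cost is SAP wording, a few table columns and one degree of freedom per model. Item 1 needs no new data. Item 2 needs none with APACHE IV; with ARDS category, first confirm that the entry PaO2/FiO2 is recorded in the database. Randomization is unchanged. If sections outside the synopsis already specify such an analysis, a cross-reference is enough.
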